4.2 Screening and pre-treatment criteria

4.2.1 Recruitment

Patients will be recruited through the head and neck oncology clinic at Sidney Kimmel Comprehensive Cancer Center at Johns Hopkins (SKCCC) including medical oncology, radiation oncology, multidisciplinary, dental/ oral surgery and head and neck surgical oncology. Each enrolled subject will be assigned a participant sequential subject number at the time of consent with site number assigned in advance, e.g., 1-001, 1-002, etc.

4.2.2 Determination of Eligibility

After eligibility is established, the study staff will register participants. The following are required to be submitted for successful registration:

- Copy of subject consent
- Copies of the following documents:
 - Diagnostic pathology reports (with HPV status for oropharyngeal SCC)

- Pathology report(s) from initial diagnosis
- Pathology report(s) from the recurrence
- Baseline cross-sectional imaging (as clinically indicated, report sufficient for enrollment)
- Laboratory reports including:
 - Complete blood count (CBC) with differential (including absolute lymphocyte count) and direct platelet count.
 - Chemistry: Albumin, SGOT (AST), SGPT (ALT), Bilirubin, Calcium, Creatinine, Glucose, Total protein, Urea nitrogen, Electrolytes (including sodium, potassium, chloride and bicarbonate).
 - Baseline thyroid function assay: Thyroid Stimulating Hormone (TSH). Abnormal endocrine results should be followed up per standard of care, and may require an endocrine consult and additional testing.
- Medical records documenting treatment history of the initial therapy for SCCHN before recurrence
- Other documents, if requested.

Study treatment cannot begin until the patient is registered and assigned to a treatment cohort.

Subjects who sign a consent form but do not initiate protocol treatment for any reason (e.g., subjects who are screen failures), and patients who do not undergo surgical resection will be replaced and will not count towards our accrual goal of 26 patients (Patient allocation ideally should be 1:1 between both cohorts but may vary). All patients who receive a dose of nivolumab will be evaluable for safety and feasibility.

4.2.3 Pre-treatment criteria

Enrolled patients will need to meet the following criteria before receiving nivolumab.

| | |
|--|--|
| leukocytes | ≥ 1,500/mcL |
| absolute neutrophil count | ≥ 1,000/mcL |
| platelets | ≥ 100,000/mcL |
| total bilirubin | ≤ 1.5 X institutional upper limit of normal (except subjects with Gilbert syndrome, who can have total bilirubin < 3.0 mg/dL) |
| AST(SGOT)/ALT(SGPT) | ≤ 3 X institutional upper limit of normal |
| Creatinine OR creatinine clearance | within normal institutional limits OR ≥ 40 mL/min (using modified Cockcroft-Gault formula) for patients with creatinine levels above institutional normal. |

4.2.4 Diagnostic and surgical evaluations

All patients enrolled on this protocol must be surgical candidates with either locally recurrent SCCHN or oligometastatic SCCHN. Patients will have undergone radiographic evaluation indicating no evidence of disease outside the planned surgical field and main/target lesion/s should be determined to be amenable for resection by the treating surgeon.

Distant metastatic disease is permissible if a clinical indication for surgery exists (e.g. in order to provide symptom control) and such distant disease can be addressed at an interval with systemic therapy (e.g. chemotherapy, targeted therapies, etc), or local therapies (e.g. radiation, metastatectomy) as clinically indicated.

Any further preoperative testing that is recommended by the surgeon or anesthesiologist will be performed as part of standard of care. Surgery for patients enrolled on this protocol will be according to generally accepted standards of care. Patients should have baseline imaging as clinically appropriate of the affected area (neck/chest/abdomen and/or pelvis) – e.g. a CT or MRI with IV contrast and appropriate imaging should be repeated after completing neoadjuvant therapy, within the 7 days prior to planned surgery to assess response.

4.3 Study drug administration

Patients will receive 1 dose of nivolumab on approximately Day -28 prior to planned surgery on or after Day 0 and up to/including Day +14. A 14 day window is allowable (as needed for scheduling purposes, or if clinically appropriate for patients with clinical benefit/improvement, if deemed safe by the treating physicians (surgeon & medical oncologist). Furthermore if clinically indicated patients may undergo surgery earlier (see Section 4.1.2 regarding early surgery, salvage treatment).

Nivolumab is to be administered as a 30 minute IV infusion.

Nivolumab may be diluted in 0.9% Sodium Chloride Solution or 5% Dextrose solution. All subjects will receive nivolumab at a flat dose of 480 mg IV.

Please refer to the current nivolumab investigators brochure for storage conditions. Recommended safety measures for preparation and handling of nivolumab include laboratory coats and gloves.

For additional details on prepared drug storage and use time of nivolumab under room temperature/light and refrigeration, please refer to the BMS-936558 (nivolumab) current Investigator Brochure section for “Recommended Storage and Use Conditions”. There will be no dose escalations or reductions of study drugs allowed. There are no premedications recommended for nivolumab on the first dose.

4.4 Management of Nivolumab -related infusion reactions

Since nivolumab contains only human immunoglobulin protein sequences, it is unlikely to be immunogenic and induce infusion or hypersensitivity reactions. However, if such a reaction were to occur, it might manifest with fever, chills, rigors, headache, rash, pruritis, arthralgias, hypo- or hypertension, bronchospasm, or other symptoms.

All Grade 3 or 4 infusion reactions should be reported as an SAE if criteria are met. Infusion reactions should be graded according to NCI CTCAE (Insert version e.g.: 4.0) guidelines.

Treatment recommendations are provided below and may be modified based on local treatment standards and guidelines as appropriate:

Grade 1 symptoms: (Mild reaction; infusion interruption not indicated; intervention not indicated)

Remain at bedside and monitor subject until recovery from symptoms. The following prophylactic premedications are recommended for future infusions: diphenhydramine 50 mg (or equivalent) and/or paracetamol 325 to 1000 mg (acetaminophen) at least 30 minutes before additional nivolumab administrations.

Grade 2 symptoms: (Moderate reaction requires therapy or infusion interruption but responds promptly to symptomatic treatment [eg, antihistamines, non-steroidal anti-inflammatory drugs, narcotics, corticosteroids, bronchodilators, IV fluids]; prophylactic medications indicated for 24 hours).

Stop the nivolumab infusion, begin an IV infusion of normal saline, and treat the subject with diphenhydramine 50 mg IV (or equivalent) and/or paracetamol 325 to 1000 mg (acetaminophen); remain at bedside and monitor subject until resolution of symptoms. Corticosteroid or bronchodilator therapy may also be administered as appropriate. If the infusion is interrupted, then restart the infusion at 50% of the original infusion rate when symptoms resolve; if no further complications ensue after 30 minutes, the rate may be increased to 100% of the original infusion rate. Monitor subject closely. If symptoms recur then no further nivolumab will be administered at that visit. Administer diphenhydramine 50 mg IV, and remain at bedside and monitor the subject until resolution of symptoms. The amount of study drug infused must be recorded on the electronic case report form (eCRF). The following prophylactic premedications are recommended for future infusions: diphenhydramine 50 mg (or equivalent) and/or paracetamol 325 to 1000 mg (acetaminophen) should be administered at least 30 minutes before additional nivolumab administration. If necessary, corticosteroids (recommended dose: up to 25 mg of IV hydrocortisone or equivalent) may be used.

Grade 3 or Grade 4 symptoms: (Severe reaction, Grade 3: prolonged [ie, not rapidly responsive to symptomatic medication and/or brief interruption of infusion]; recurrence of symptoms following initial improvement; hospitalization indicated for other clinical sequelae [eg, renal impairment, pulmonary infiltrates]).

Immediately discontinue infusion of nivolumab. Begin an IV infusion of normal saline, and treat the subject as follows. Recommend bronchodilators, epinephrine 0.2 to 1 mg of a 1:1,000 solution for subcutaneous administration or 0.1 to 0.25 mg of a 1:10,000 solution injected slowly for IV administration, and/or diphenhydramine 50 mg IV with methylprednisolone 100 mg IV (or equivalent), as needed. Subject should be monitored until the investigator is comfortable that the symptoms will not recur. Nivolumab will be permanently discontinued. Investigators should follow their institutional guidelines for the treatment of anaphylaxis. Remain at bedside and monitor subject until recovery from symptoms. In the case of late-occurring hypersensitivity symptoms (eg, appearance of a localized or generalized pruritis within 1 week after treatment), symptomatic treatment may be given (eg, oral antihistamine, or corticosteroids).

4.5 Surgical resection

4.5.1 Surgery for SCCHN patients with newly diagnosed and untreated locoregional disease: Cohort 1
Extent of primary surgery and reconstruction will be decided by treating surgeons following the best clinical practice.

4.5.2 Surgery for SCCHN patients with locoregionally recurrent or oligometastatic disease: Cohort 2
Salvage local surgery is a standard practice for patients with resectable locoregional recurrence. Metastatic disease is permissible and can be addressed with systemic or local therapies (radiation, surgery etc), at an interval as clinically indicated in addition to the local treatment. Surgical technique and extent will be decided by treating surgeons following the best clinical practice.

4.6 Adjuvant treatment post surgery

Postoperative radiotherapy with or without concurrent chemotherapy for subjects in both cohorts (cohort 1 and 2) will be determined based upon pathologic assessment and administered at the discretion of the treating multidisciplinary team based on established standard of care. Common scenarios indicating radiotherapy with concurrent chemotherapy may include high-risk pathologic findings such as positive margin or extranodal extension. Decision for or against postoperative radiotherapy with or without concurrent chemotherapy will be recorded.

4.7 Evaluation of peri-operative safety

Subject safety will be assessed at the regular trial safety meeting and adhoc as part of clinical care (including at the weekly tumor board with the surgeons) from the start of therapy until 100 days after the last dose of study treatment, or 30 days following surgery, whichever is longer, for information regarding operative complications including treatment-related delay in planned surgery and in particular potential immune related toxicities (Note: Only those subjects who initiate protocol treatment will be followed). Toxicities will be reviewed at regular meetings of study investigators and research staff and minutes of these meetings will be documented by the clinical research staff. In the event that a subject does not continue his or her peri-operative care at the institution, every attempt will be made to collect this information either by direct contact or through communication with the

Johns Hopkins Protocol #: J1923

subjects outside physician(s).

4.8 Discontinuation, withdrawal and replacement of subjects

All patients who receive at least one dose of study treatment (including those who do not undergo surgical resection of their tumor) will be included in the overall evaluation of safety (intention-to-treat analysis). All reasons for discontinuation of therapy should be documented clearly in the medical record. If a subject discontinues or withdraws from the study, every attempt will be made to obtain an off-study blood collection if the subject is able and willing to do so.

Subjects who do not undergo surgical resection of their tumor, while evaluable for safety and feasibility, will not be evaluable for the key secondary endpoint of pathologic response. Subjects who sign a consent form but do not initiate protocol treatment for any reason (e.g., subjects who are screen failures), and patients who do not undergo surgical resection (for reasons unrelated to the study drug or toxicity) will be replaced and will not count towards our accrual goal.

4.9 Discontinuation of treatment

The reasons for discontinuation of protocol treatment include:

- Evidence of significant disease progression during the preoperative phase at the discretion of the treating investigator.
- Non-compliance with the study protocol; including, but not limited to not attending the majority of scheduled visits. The principal investigator will determine when non-compliance should lead to removal from study. **Note:** The patients will still be included in the overall evaluation of safety (intent-to-treat analysis).
- Unacceptable toxicity. **Note:** The patients will still be included in the overall evaluation of safety (intent-to-treat analysis).
- Intercurrent illness or condition that would, in the judgment of the treating investigator, affect assessment of clinical status to a significant degree or require discontinuation of study treatment.
- At subject's own request. **Note:** The reason for discontinuation from the study must be documented. The patients will be included in the overall evaluation of safety (intent-to-treat analysis) if any protocol therapy was administered prior to withdrawal.
- Study is closed for any reason (e.g. new information shows that the patient's welfare would be at risk if he or she continued study treatment).

4.10 Study calendar

| Procedure | Screening (Days -42 to -29) ^a | Day -28 | Pre- surgical evaluation (Days -7 to -1)** | Day 0 Surgery (up to day +14) | Post- surgical evaluation (Days 21 to 42) | Follow-up visits (Every 3-4 months for 1 yr; then every 6 months for 2nd yr.) ^{\$\$} | At the time of recurrence | Survival Follow-up (every 12 months) |
|--|--|------------|--|---|---|---|---------------------------------|---|
| Clinical Assessments | | | | | | | | |
| Physical Exam | X | X | X | | X | X | X | |
| Vital Signs | X | X | X | | X | X | X | |
| Performance status (ECOG) | X | X | X | | X | X | X | |
| Concomitant medicines | X | X | X | | X | X | X | |
| Toxicity assessments | X | X | X | | X | X | X | |
| Electrocardiogram (EKG) | X | | | | | | | |
| Laboratory Tests | | | | | | | | |
| CBC with diff | X | X**** | X | | X | X | X | |
| Chemistry including LFT | X | X**** | X | | X | X | X | |
| # IF abnormal LFTs draw: Hepatitis B/C serology | (X) [#] | | | | | | | |
| TSH | X | | | | X | X | | |
| Free T4 and T3 | X | | | | | | X | |
| PT/INR and PTT | X | | X | | | | X | |
| Pregnancy Tests (WOCBP only) | X | | X | | X | | X | |
| Treatment | | | | | | | | |
| Nivolumab | | X | | | | | | |
| CT neck/chest with IV contrast* | X | | X | | | (X) | (X) | |
| MRI neck with IV contrast, optional† | (X) | | (X) | | | (X) | (X) | |

| Procedure | Screening (Days -42 to -29) | Day -28 | Pre- surgical evaluation (Days -7 to -1) | Day 0 (and up to day +14) Surgery | Post- surgical evaluation (Days 21 to 42) | Follow-up visits (Every 3- 4 months for 1 yr; then every 6 months for 2nd yr.) ^{§§} | At the time of recurrence | Survival Follow-up (every 12 months) |
|---|-----------------------------------|----------------|--|---|---|---|---------------------------------|---|
| Correlative Blood/Tissue/Stool Studies | | | | | | | | |
| PBMCs, Serum, plasma (Blood collection 100 cc's) | | X ^b | | X | X | X | X | |
| Tumor biopsy/sample | X | | | X (resection specimen) | | | X | |
| Stool Sample | | X ^c | X | | X | X | X | |
| Oral Rinse ^d | | X | | | X | X ^d | X | |
| Medical & Dietary Questionnaire | | X | | | X | X | X | |
| Survival | | | | | | | | X |

- a. screening labs are permitted to be used for treatment if completed within three (+3) days of day -28
- b. Research blood permitted to be collected anytime after consent and prior to Nivolumab infusion (Days -42 to day -28)
- c. Patients are to be provided with a stool collection kit during screening (days -42 to -29) and instructed to collect a stool sample within 48 hours of their scheduled infusion day (day -28).
- d. Oral rinse is considered an optional collection during the first and second year follow up visits.

*CT abdomen/pelvis can be added if there's a clinical indication. MRI may replace or supplement CT scans if clinically appropriate.

Ideally same imaging modality should be used for sequential imaging assessments.

** can be done on day of surgery also if necessary.

† MRI can be used at the treating physician's discretion; ideally same modality should be used throughout.

(X) as clinically indicated

*** Blood for correlates may be collected anytime after consent and prior to Nivolumab infusion.

Johns Hopkins Protocol #: J1923

***** Days -42 until/including Day -28

\$\$ F/u visits are allowable +/- 28 days or as clinically indicated

[See Appendix D](#) for Sociodemographic Characteristics Questionnaire

5. DOSE DELAY AND TOXICITY MONITORING

Dosing delays will not be permitted for this study. Prior to surgery, any treatment related toxicity should have resolved to \leq Grade 2. Decision for surgery should be made by the treating medical oncologist and the surgeon.

General management algorithms for potential nivolumab-related toxicities are contained in Appendix of this protocol and in the Investigators Brochure.

5.1 Dose-Limiting Toxicity

Dose-Limiting toxicity (DLT) is defined as any of the items listed below that occur from the first dose of nivolumab through day 100 following the last dose of nivolumab (or day 30 post surgery, whichever is longer). Any patient who experiences a DLT will proceed to surgery after standard preoperative evaluation by a surgeon and anesthesiologist.

- Any \geq Grade 2 drug-related pneumonitis or interstitial lung disease that does not resolve to Grade 0 or 1 within 2 weeks with systemic steroids. The management algorithm for pneumonitis or pulmonary toxicity can be found in the appendix of current Investigator Brochure for nivolumab
- Any \geq Grade 2 drug-related uveitis or eye pain that does not respond to topical therapy and does not improve to Grade 1 severity within the retreatment period OR requires systemic treatment. If uveitis occurs during nivolumab treatment, workup and treatment should follow the nivolumab uveitis toxicity treatment algorithm located in the appendix of the nivolumab Investigators Brochure.
- Any Grade 3 non-skin drug-related adverse event lasting \geq 7 days with the exception of asymptomatic laboratory abnormalities.
- Grade 3 drug-related bronchospasm, allergic reaction, or infusion-related reaction will be recorded and treated; however, it will not count as a dose-limiting toxicity for study purposes.
- Any Grade 3 drug-related diarrhea that does not respond to dose delay and the use of systemic steroids within 2 weeks. If diarrhea occurs during nivolumab treatment, workup and treatment should follow the nivolumab diarrhea toxicity treatment algorithm located in the appendix of the nivolumab Investigators Brochure.
- Any Grade 4 drug-related adverse event, including laboratory abnormalities apart from isolated Grade 4 electrolyte imbalances/abnormalities that are not associated with clinical sequelae and are corrected with appropriate management within 72 hours of their onset.
- Any of the following drug-related hepatic function laboratory abnormalities or potential Drug Induced Liver Injury (DILI):
 - AST or ALT $> 5-10x$ ULN for > 2 weeks

- AST or ALT >10x ULN
- Total bilirubin > 5 x ULN
- Concurrent AST or ALT >3 x ULN and total bilirubin >2 x ULN
- If suspected DILI occurs, workup and treatment should follow the nivolumab DILI treatment algorithm located in the appendix of the nivolumab Investigators Brochure.
- Any other toxicity which is assessed by the principal investigator as having directly led to a delay in surgical resection more than 28 days past the planned Day 0 (or 14 days past D +14).
- Failure to complete all protocol specified treatment doses due to toxicity (at the discretion of the PI).

Note - Adverse events of special interest are nivolumab-related events with potential immune-mediated causalities. For example, this may include cutaneous toxicities, colitis, liver function abnormalities (AST, ALT, total bilirubin, alkaline phosphatase), endocrine abnormalities (hyperthyroidism, hypothyroidism, hypophysitis and secondary adrenal insufficiency), interstitial pneumonitis and nephritis. These events will be noted. However, it may not constitute DLT's unless they fulfill the previously outlined DLT criteria described above.

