10. STATISTICAL CONSIDERATIONS

10.1 Study Design/Endpoints

10.1.1 Study Design

Patients will receive 1 dose of nivolumab, 480mg IV on Day -28 prior to planned surgery on or after Day 0 and up to/including Day +14. A 14 day window is allowable (as needed for scheduling purposes, or if clinically appropriate for patients with clinical benefit/improvement, if deemed safe by the treating physicians (surgeon & medical oncologist). Furthermore if clinically indicated patients may undergo surgery earlier (see Section 4.1.2 regarding early surgery, salvage treatment).

Patients will be observed for **perioperative grade 3-4 adverse events through day 100 (or day 30 post surgery – whichever is longer)** following the last dose of study drug(s). Safety and feasibility will be monitored continually throughout the study through biweekly meetings with investigators. A set of markers of immune reactivity measured in the tumor resection specimens, draining lymph nodes, and peripheral blood will be evaluated. Feasibility in this study means the successful completion of preoperative treatment and proceeding to surgery without any extended treatment related delays. Extended treatment-related delay is defined as > 28 days from preplanned Day 0 in this context (or accordingly >14 days from day +14).

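### Sections 5 and 5.1 give different instructions on surgery for a patient whose DLT is still at Grade 3-4 at the planned operation, and nothing says which governs

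*Combined protocol and SAP*

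**What the plan says.** Section 5 (Dose Delay and Toxicity Monitoring) sets a general condition: "Prior to surgery, any treatment related toxicity should have resolved to" Grade 2 or lower. It then assigns responsibility: "Decision for surgery should be made by the treating medical oncologist and the surgeon".

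Section 5.1 (Dose-Limiting Toxicity) says: "Any patient who experiences a DLT will proceed to surgery after standard preoperative evaluation by a surgeon and anesthesiologist". It names no grade, gives no timing and does not refer back to Section 5.

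The DLT list in Section 5.1 includes events above Grade 2. One item begins "Any Grade 3 non-skin drug-related adverse event lasting" and sets a minimum of 7 days; another begins "Any Grade 4 drug-related adverse event, including laboratory abnormalities", with an exception for isolated electrolyte abnormalities corrected within 72 hours. DLTs count if they "occur from the first dose of nivolumab through day 100 following the last dose of nivolumab", or to 30 days after surgery if that is longer, so the window covers time before and after the operation. The list also makes a DLT of any other toxicity that the principal investigator judges to have directly delayed resection by more than 28 days past Day 0.

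Feasibility, part of the primary endpoint, means completing preoperative treatment and reaching surgery without an extended treatment-related delay. Section 10.1.1 gives the limit: "Extended treatment-related delay is defined as > 28 days from preplanned Day 0 in this context". Section 10.2 counts feasibility over all patients who received a dose of nivolumab.

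**The concern.** The Section 5.1 sentence covers the patients for whom the Section 5 condition matters most. If a DLT is still at Grade 3 or 4 when surgery is due, a reader of Section 5 would hold surgery until the toxicity falls to Grade 2 or lower. A reader of Section 5.1 would send the patient on after preoperative evaluation. Two investigators could handle the same patient differently and each cite the protocol.

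What is at stake is first the safety of a patient with ongoing severe toxicity who is facing major surgery. There is also a possible effect on a primary endpoint. A patient operated on within the limit is a feasibility success, while one who waits past the limit, or is never operated on because of toxicity, is a failure. The conflict can therefore decide how a patient is counted, but only in that situation.

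**Working it through.** **Step 1. Where the two sections differ.** The Section 5 condition is Grade 2 or lower; Section 5.1 has no grade condition.

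| State of the DLT at planned surgery | Section 5 | Section 5.1 | Conflict |
|---|---|---|---|
| Persistent Grade 2 (for example pneumonitis or uveitis) | Condition met | Proceeds | No |
| Resolved before surgery | Condition met | Proceeds | No |
| Starts after surgery | Not applicable | Not applicable | No |
| Still Grade 3 or 4 | Condition not met | Proceeds after evaluation | Yes |

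No section states an order of precedence.

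**Step 2. When the feasibility count changes.** Dosing is on about Day -28 and the delay limit is Day +28. Waiting turns a success into a failure only if surgery falls more than 28 + 28 = 56 days after dosing, or does not take place. A shorter wait leaves the count unchanged. The delay criterion in the DLT list needs the same length of delay. A patient who already has a DLT would not be counted twice in a proportion of patients, so that route adds little.

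**Step 3. Reproduce the plan's feasibility figures (Section 10.2, n = 12, Clopper-Pearson).**
- 12/12: lower limit = 0.025^(1/12) = 0.735, upper limit 1, giving 73.5-100%. This matches the plan.
- 11/12: the lower limit solves P(X ≥ 11 | p) = 0.025, so p = 0.615; upper limit = 0.975^(1/12) = 0.998. This gives 61.5-99.8% and matches the plan.

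**Step 4. Effect of reclassified patients (illustrative).**
- One patient: 100% to 91.7%, a change of 1/12 = 8.3 points. The lower limit falls by 73.5 - 61.5 = 12.0 points.
- Two patients: 10/12 = 83.3% (51.6-97.9%).

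**Step 5. Effect on the feasibility stopping rule (Table 2).** The prior is Beta(0.1, 0.9) and the halt criterion is P(risk > 25%) ≥ 0.70. After r delays in n patients the posterior is Beta(0.1 + r, 0.9 + n - r). With r = 2 the posterior probability is 0.95, 0.87 and 0.77 for n = 2, 3 and 4, so two delays among the first 2-4 patients reach the boundary. The boundary recomputes exactly for n = 2 to 12. Its smallest count is 2, so one affected patient never triggers a halt alone.

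**Step 6. How often this could arise.** The documents give no rate of Grade 3-4 toxicity unresolved at planned surgery. The nearest figure is the Section 10.2 assumption that at most 5% of patients have a drug-related event of Grade 3 or higher. At 5%:
- expected patients with any such event per cohort: 12 × 0.05 = 0.6;
- chance of at least one in 12: 1 - 0.95^12 = 46.0%;
- if every such event caused an extended delay, chance of two or more in the first four: 1 - 0.95^4 - 4 × 0.05 × 0.95^3 = 1.4%; chance of crossing Table 2 at any point up to 12 patients: 1.7%.

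On that assumption these are ceilings, since only some such events would be unresolved at planned surgery, and fewer still would delay it past Day +28.

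**The case against.** The strongest reply is that the passages can be read together. Section 5.1 sits under Section 5, whose condition covers all treatment-related toxicity and so includes DLTs. The Section 5.1 sentence gives no timing and could mean only that a DLT does not by itself cancel surgery. The DLT list expects toxicity to delay some operations, and Sections 4.1 and 4.8 limit replacement to patients who miss surgery for reasons unrelated to toxicity, which implies that toxicity may keep some from it. A reader might therefore go too far in inferring that the protocol orders surgery on schedule despite ongoing severe toxicity; the documents do not say that. The joint reading is possible, but Section 5.1 does not state it: the sentence is unconditional, names its own precondition and does not point back to Section 5.

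Three further limits stand. Section 5 says that toxicity should have resolved, which is softer than a requirement. The named roles need not clash, because deciding on surgery (medical oncologist and surgeon) differs from preoperative evaluation (surgeon and anesthesiologist); the text only fails to say how they fit together. And 8.3 points is what any one reclassified patient in 12 would produce; it does not measure how often this ambiguity would bite.

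**Conclusion.** The inconsistency is real but narrow. As written, the two sections diverge for a DLT still at Grade 3-4 at planned surgery, and nothing sets precedence. The main consequence is patient safety.

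A reader might infer that every ongoing DLT is affected, or that these patients decide the feasibility result. The documents support neither. Persistent Grade 2, resolved and post-surgical DLTs fall outside the conflict, and the count moves only if surgery passes Day +28 or does not happen. The shift from 12/12 to 11/12 assumes one such patient in a cohort of 12. The plan's confidence intervals and stopping boundary are themselves correct.

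**What to change.** Reconcile Sections 5 and 5.1 so that one stated condition applies before surgery to all patients, including those with a DLT. State how the surgical decision and the preoperative evaluation fit together and who is responsible for each. The clinical team should decide the content of the condition; no view is taken here on which rule is right. The cost is a wording amendment to the two sections. Sample size, endpoint definitions and stopping boundaries need no change for this point.
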